Protocol Title: Prospective Randomized Control Trial of Open versus Robotic REtrOmuscular Ventral Hernia repair [ORREO Trial]

NCT: 03007758

Date: 07 Apr 2017

ORREO Trial Protocol:

Date: 07Apr2017

Title: Prospective Randomized Control Trial of Open versus Robotic REtrOmuscular Ventral Hernia repair [ORREO Trial]

PI: [name]

Co-I: [name], DO
[name], APRN, NP-C

Background:

Due to the variety of hernia repair techniques and materials available, and the heterogeneity of the hernia patient population, there is no consensus standard of care for ventral hernia repair. The Rives-Stoppa retromuscular hernia repair is considered by many the standard by which all other techniques should be compared {Israelsson:2006gn}{Helgstrand:2013ev}. There is good long term data on this technique, with overall recurrence rate of 7.4% and wound complication rates of 9.3% (3). Unfortunately, many factors that lead to development of ventral and incisional hernias are also those that increase the risk of recurrence and wound morbidity. Obesity, COPD, DM, and tobacco abuse are particularly troublesome conditions that confer higher morbidity after abdominal wall reconstruction (AWR). While preoperative weight loss and smoking cessation are modifiable risk factors, many patients will not successfully lose weight, are not eligible for bariatric surgery, will not stop smoking, and are at risk for developing increasingly complex hernias or presenting with acute incarceration requiring urgent repair.

Since its initial description, laparoscopic ventral hernia repair (LVHR) was quickly adopted and has been shown to significantly decrease wound morbidity, with comparable recurrence rates (2) (3) (4). Though our preferred technique is an open retromuscular VHR (OVHR), laparoscopy remains an important technique for high risk patients. However, the hernia defect itself is typically not closed, which can result in pseudorecurrence and eventration of the mesh through the hernia defect, particularly with larger defects (5). Additionally, mesh placed in the intraperitoneal position has the potential to complicate subsequent abdominal operations, with incidence of unplanned enterotomy or bowel resection as high as 20% (6) (7).

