The development of our robotic retromuscular ventral hernia repair (RRVHR) technique combines the benefits of the OVHR (reconstruction of native anatomy and a functional abdominal wall, placement of mesh in the retromuscular space) with those of LVHR (lower wound morbidity). Understandably, during the early development of a novel technique, we have been highly selective of our patients, typically selecting those we deem to have a high chance of a successful repair, and those with small to moderate defects as we refined the technical details of the operation. As our experience has increased and technique refined, we have been able to repair more complex patients with larger, more complex hernia defects. We

anticipate that these patients with the highest risk of wound morbidity will have the greatest clinical benefit from the robotic approach.

We describe a novel surgical technique, using new technology to duplicate the abdominal wall reconstruction achieved with OVHR in a minimally invasive fashion. While the feasibility of robotic VHR has been described, previous reports describe essentially a LVHR with intraperitoneal mesh placement utilizing the robot rather than a laparoscope. The only other report of a similar technique, and the inspiration of our development of RRVHR, is a transabdominal, retromuscular repair of umbilical hernia with plication of diastasis rectus described by [name] (8). The ability to duplicate a complete abdominal wall reconstruction with mesh reinforcement in high risk patients using a minimally invasive technique is a significant step forward in improving the outcomes in VHR. To our knowledge, we have the largest experience with this technique and the first reported outcomes data, which were presented at the World Hernia Congress, April 2015 (10).

Purpose:

The purpose of this study is to determine how the robotic retromuscular hernia repair compares to the open retromuscular hernia repair for large hernia defects in patients at higher risk of wound complications.

Hypothesis:

We hypothesize that the robotic retromuscular ventral hernia repair improves the clinical composite outcome, as compared to open retromuscular hernia repair, in high risk patients.

Primary Endpoints:

1. Composite Outcome (See full description below)
 - a. Surgical Site Occurrence (excluding simple seroma)
 - b. Surgical Site Infection
 - c. Hospital Readmission
 - d. Hernia Recurrence

Secondary Endpoints:

1. All Surgical Site Occurrences

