2. Surgical Site Occurrences requiring procedural intervention
3. All Surgical Site Infections
4. Surgical Site Infections requiring procedural intervention
5. Length of Stay
6. Operative Time
7. Quality of Life
8. Cost

Composite Outcome:

In order to adequately power this study and provide a clinically relevant outcome measure, a composite outcome was designed to capture the outcomes that are considered clinically

significant. As such, simple seroma, which is very common, is excluded. Any seroma requiring procedural intervention will be included. Management of seroma or hematoma requiring intervention is discussed below under “Management of Complications.” Other SSOs, such as skin dehiscence, cellulitis, hematoma or skin necrosis, are included as these are more likely to require some intervention, such as local wound care or drainage, or some additional cost, such as antibiotic therapy. Similarly, SSIs frequently require additional intervention and cost.

Study Design:

Prospective randomized control trial of robotic retromuscular ventral hernia repair versus open retromuscular ventral hernia repair in patients at high risk for adverse outcome. [Open versus Robotic REtrOmuscular Incisional hernia repair; ORREO trial]

Patient Selection:

All patients presenting to the Greenville Health System Hernia Center who meet the inclusion criteria will be considered for enrollment. Patients who agree to participate will be randomized to robotic retromuscular ventral hernia repair (group 1, RRVHR) or open retromuscular ventral hernia repair (group 2, OVHR). Randomization will occur in the office setting to allow appropriate scheduling of the case.

Participant Enrollment: 50 patients per study group (100 patients total)

Inclusion Criteria:

>18 years old

Ventral or incisional hernia measuring $\geq 7\text{cm}$ and $\leq 15\text{cm}$

At least one of the following risk factors:

BMI >30

COPD

DM

Current smoker (within 1 month)

Exclusion Criteria:

Current abdominal or abdominal wall infection

Presence of ileostomy, colostomy, or ileal conduit

CDC wound class 3 or 4

Hernia defect $< 7\text{cm}$ or $>15\text{cm}$

Pregnant women will be excluded from participating in this study.

Methods:

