Prospective randomized control trial of robotic retromuscular ventral hernia repair versus open retromuscular ventral hernia repair in patients at high risk for adverse outcome. [Open versus Robotic REtrOmuscular Incisional hernia repair; ORREO trial]. Patients who agree to participate will be randomized to robotic retromuscular ventral hernia repair (group 1, RRVHR) or open retromuscular ventral hernia repair (group 2, OVHR). Randomization will be performed using the randomize function in the Redcap database.

Data Collection:

All patients will be entered prospectively into the Americas Hernia Society Quality Collaborative (AHSQC) database and followed prospectively. For data points that will be collected for trial purposes that are not contained within the AHSQC dataset, a Redcap database will be used.

Within the AHSQC, the following data is collected: Preoperative Patient Reported Outcomes via a validated, hernia specific quality of life questionnaire. Demographic data include age, sex, ethnicity, zip code, and insurance coverage. Patient characteristics include DM, COPD, HTN, immunosuppression, smoking status, hepatic disease, renal disease, antiplatelet or anticoagulant therapy, height/weight/BMI, history of previous hernia repair (including number of repairs, type of repair, type of mesh), history of previous abdominal wall infection, and functional status. Operative details include hernia width, height, presence of prior mesh, operative time, mesh selection, size of mesh placed, position of mesh placement, choice of mesh fixation, ability to close the midline fascia, technique for closure, use of component separation technique, and intraoperative complications. Hospital data will include LOS and any acute medical complications. Postoperative follow-up will occur at 2 weeks, 6 weeks, 6 months, 1 year, and 2 years. Patient Reported Outcomes will be collected at each of these post-operative visits. Cost data will be obtained from the Greenville Health System office of Business Intelligence after discharge from the index hospital stay, and include any readmission or additional procedural intervention.

Additional data not contained within the AHSQC, including patient account number, total operative time in minutes, total anesthesia time, and EBL, will be collected prospectively and recorded at the time of surgery completion. Operative time will be recorded as total anesthesia time and total operative time.

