Will be assess via AHSQC Patient Reported Outcomes Quality of life questionnaire will be administered at preoperative visit and each planned postoperative visit, and will be administered by the Study Coordinator, Principal Investigator or Co-Investigator.

Sample Size & Statistical Analysis

Based on our current RRVHR outcomes and utilizing our entire OVHR database, which is maintained in a prospective fashion, we obtained a composite outcome using the combination of SSO (excluding seromas), SSI, hospital readmission, and hernia recurrence. For OVHR, the incidence of the composite outcome is 52.2% and for RRVHR 24.1%. Using a power of 80% and a significance of 5%, we estimate that 46 patients enrolled in each arm will demonstrate a difference in our primary endpoint. We plan to enroll at least 50 patients in each arm to allow for potential patient withdrawal or failure to maintain follow-up.

Differences in discrete primary and secondary outcomes (SSO, SSI, readmission, recurrence) between the OVHR and RRVHR groups will be analyzed using Chi-squared tests, or Fisher's Exact Test for small sample sizes ($N \leq 6$). Differences in continuous outcomes (length of stay, operative time, and costs) between the OVHR and RRVHR groups will be determined using Students t-test and Mann-Whitney U tests. P-values <0.05 will be considered indicative of statistical significance. All analysis will be completed using R statistical software (R version 3.0.2).

Adverse Events: Defined as any unfavorable or any unintended sign, symptom or disease that is reported by the patient to have occurred, or a worsening of a preexisting condition. Adverse events will be recorded and detailed.

Potential Risks:

The following are possible complications specific to hernia repair, and may occur after either open or robotic repair:

- **Seroma:** A seroma is a collection of watery fluid below the skin that occurs in the space that is separated during surgery or in the space where your hernia was. This occurs in up to 50% of patients. This is almost always treated with observation. If treatment is needed, a small needle or tube may be placed to drain the fluid.

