- Venous thromboembolism (blood clot): Blood may clot within the vessels of the body, causing swelling of the leg(s). This occurs in about 2% of patients. If the blood clot breaks free from the vessels, they can travel to the vessels in the lungs, which can be fatal. Fatal blood clots are rare events. A blood thinner is needed for treatment. You will be given an injection of a blood thinner prior to the operation, as well as devices that will squeeze your calves, in order to prevent you from getting any blood clots.
- Respiratory complications, such as pneumonia or difficulty breathing. In rare cases, this may require you to be placed on a ventilator, a machine that assists in breathing, for a short period of time.
- Heart complications, such as heart attack, irregular heart rhythm, or heart failure.
- Ileus, which is a slowness of your intestine that may cause nausea or vomiting, may occur in 5-10% of cases. Treatment may require a tube placed through your nose to help empty your stomach.

Some of the questions in the quality of life questionnaire are of a personal nature and may be upsetting to some participants. Participants do not have to answer any questions that they do not want to answer.

This study may involve unknown risks to an unborn or nursing child. Women who are pregnant or nursing child may not participate in this study.

The study records are considered confidential, but absolute confidentiality cannot be guaranteed. This study may result in presentations and publications, but steps will be taken to make sure participants are not identified by name.

Potential Benefits:

It is not possible to know if there will be any potential benefit beyond what is expected for treatment utilizing the standard of care.

Potential Limitations:

Based on our current data, there is a shorter length of stay with robotic hernia repair compared to open, even though the remaining outcome measures (SSO, SSI, recurrence, SSOPI, SSPI, readmission) are similar, which may bias patients against opting into randomization. This may not impact clinical outcomes, but could prolong the enrollment period. Patients may also be biased in favor of, or against, robotic repair based on patients' preconceived notion of either robotic or minimally invasive surgery.

Participant withdrawal: Participants may refuse to participate or choose to withdrawal from the study at any time without fear of being penalized or losing benefits. Participants may be

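### The plan lets investigators administer the quality-of-life questionnaire, with no blinding described and no fixed mode of completion, so this secondary comparison is open to measurement bias of unknown direction and size

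*Combined protocol and SAP*

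**What the plan says.** Quality of life is the seventh of eight items under Secondary Endpoints ("7. Quality of Life") and is not a component of the primary composite. Data Collection calls the instrument validated and hernia-specific: "Preoperative Patient Reported Outcomes via a validated, hernia specific quality of life questionnaire".

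The Quality of Life section gives the timing, "questionnaire will be administered at preoperative visit and each planned postoperative visit", and the people responsible: the questionnaire "will be administered by the Study Coordinator, Principal Investigator or Co-Investigator". The Follow-up section lists 2 weeks, 6 weeks, 6 months, 1 year and 2 years, so the sentence governs six assessments per patient.

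On the investigators' position, the Background describes the robotic operation as their own: "The development of our robotic retromuscular ventral hernia repair (RRVHR) technique combines the benefits of the OVHR". The Hypothesis section adds: "We hypothesize that the robotic retromuscular ventral hernia repair improves the clinical composite outcome". The Background also states a preference for the comparator: "Though our preferred technique is an open retromuscular VHR (OVHR), laparoscopy remains an important technique for high risk patients".

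Patient Selection places randomisation in the office so that the case can be scheduled. Blinding of patients, surgeons or assessors is not described anywhere. The document does not mention self-completion, a script, an independent administrator or a common mode across visits.

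**The concern.** A quality-of-life score is subjective, and how it is collected can affect the answer. The plan allows it to be collected by people who know which operation was done, who may have done it, and who have a stated interest in one of the techniques. A patient may answer differently to the surgeon than to a coordinator or to a form completed alone. The section on risks acknowledges that some items are personal, may be upsetting and may be skipped, so the person present could also influence which items are answered.

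An effect that is equal in both arms cancels in the comparison. The problem arises if it differs by arm, either because the administrator's manner differs by operation or because the mix of administrators differs between arms. The plan prevents neither. Randomisation balances the patients but not a distortion introduced when the outcome is recorded, and such a distortion cannot be removed afterwards.

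**Working it through.** **Does another section close the gap?** Each possible safeguard, checked against the whole document:

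| Safeguard | What the document says |
|---|---|
| Administrator independent of the investigators | Not required; the principal investigator and co-investigators are named as options |
| Blinded administrator or patient | Not described; allocation is made in the office for scheduling |
| Self-completion | Not stated; the verb used does not settle it |
| Fixed script | Not stated |
| Same mode at all six assessments | Not stated |
| Validated instrument | Yes (Data Collection), but this does not settle who administers it or how |

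None of the first five is present, and the sixth does not replace them.

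**Is there a quality-of-life figure to check?** No. Sample Size & Statistical Analysis gives no effect size, standard deviation or sample size for it. The continuous outcomes assigned a test are length of stay, operative time and costs. The stated 46 per arm concerns the composite (52.2% versus 24.1%, 80% power, 5% significance). It reproduces with the two-sided pooled formula without continuity correction:

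- Mean proportion = (0.522 + 0.241)/2 = 0.3815.
- n = [1.960 × √(2 × 0.3815 × 0.6185) + 0.842 × √(0.522 × 0.478 + 0.241 × 0.759)]² / (0.522 − 0.241)².
- n = (1.346 + 0.553)² / 0.281² ≈ 45.7, rounded up to 46.

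That figure serves below only as a plausible number of patients per arm.

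**Illustration of size.** Three things are assumed and are not in the documents: a two-sided 5% t-test on the score, no true difference, and a collection effect δ (in SD units) that shifts every patient in one arm. The statistic is then noncentral t with 2n − 2 degrees of freedom and noncentrality δ√(n/2). At n = 46 there are 90 degrees of freedom and the critical value is 1.987.

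| δ (SD) | Noncentrality, n = 46 | False-positive rate, n = 46 | False-positive rate, n = 50 |
|---|---|---|---|
| 0.1 | 0.480 | 7.6% | 7.9% |
| 0.2 | 0.959 | 15.8% | 16.8% |
| 0.3 | 1.439 | 29.6% | 31.8% |

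The effect is diluted if investigators collect only some of the forms. If they collect half, and the effect on those is 0.1 SD, the arm-wide shift is 0.5 × 0.1 = 0.05 SD and the rate is about 5.6%, close to nominal. The result depends on δ and on that share, and the documents give neither.

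**The case against.** The strongest reply is that administering a questionnaire may mean no more than handing over a form that the patient completes. The document calls the measures patient-reported, and the instrument is validated. A reader might infer that investigators will interview patients face to face at every visit; the text does not say so. This stands, and it would lessen the bias if self-completion is intended. But the plan does not say that either, so the exposure remains.

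Four further points limit what can be claimed.

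- **Direction.** A reader might infer a bias in favour of the robotic arm. Open repair is the group's preferred technique, and the hypothesis of robotic benefit concerns the composite, not quality of life. Neither the direction nor the existence of a between-arm difference is shown.
- **Who the investigators are.** One listed co-investigator has nurse-practitioner credentials, and nothing says that this person operates or developed the technique. Not every investigator can be treated as an operating surgeon.
- **Patients' preconceptions.** The remark under Potential Limitations, "Patients may also be biased in favor of, or against, robotic repair", might be read as evidence of biased answers. It appears in a discussion of willingness to be randomised. Such preconceptions would also affect a form completed alone, so it does not support a bias from the administrator.
- **Open design.** The lack of blinding is inferred from the document's silence and from office randomisation. The document does not state it in terms.

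It is also fair to say that the absence of a named quality-of-life analysis is a more basic gap. That does not make this one harmless: an analysis can be specified late, but answers cannot be collected again.

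**Conclusion.** The concern holds in a limited form. The plan expressly permits investigators to administer a subjective secondary endpoint at all six assessments and describes no blinding, self-completion, script or common mode. That leaves an avoidable route to measurement bias.

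The documents do not establish that bias will occur, which arm it would favour or how large it would be. The rates of about 8%, 16% and 30% must not be read as estimates: they rest on an assumed test, assumed shifts and an effect on every patient in one arm, and half that exposure at the low end is close to negligible. The primary composite and its sample size are untouched by this sentence. The change is worth making because it is cheap, but it is not a condition for the trial's main conclusion.

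**What to change.** Rewrite the sentence in the Quality of Life section to state that:

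- patients complete the questionnaire themselves, on paper or electronically, before seeing the surgeon;
- the same mode is used at the preoperative visit and at all five follow-up visits;
- any help comes from the Study Coordinator, or from another team member who did not operate on that patient, using a fixed script;
- operating investigators do not administer it.

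Allowing a non-operating team member avoids excluding the nurse-practitioner co-investigator without reason. The coordinator need not be blinded for this to help, since self-completion does most of the work.

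The cost is one sentence and a short script. The Study Coordinator is already named, although the document does not describe that person's availability over two years of visits. When neither the coordinator nor another eligible person is present, the visit must rely on unaided self-completion, with a small risk of missing forms. Recording who gave help at each assessment would let that risk, and any imbalance between arms, be seen.

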- **Hematoma:** A hematoma is a collection of bloody fluid below the skin that occurs in the space that is separated during surgery or in the space where your hernia was. This may occur in about 10-15% of patients. This is almost always treated with observation. If treatment is needed, a small needle or tube may be placed to drain the fluid.
- **Skin dehiscence:** Dehiscence is a separation of the skin at the site(s) of incision(s). This occurs in less than 5% of cases. Treatment may require a gauze or possibly a vacuum dressing to be placed in the wound until it heals. Healing time will depend on the size of the area of the incision that separates.
- **Skin necrosis:** Poor blood flow to a portion of the skin may cause it to die (necrosis). This occurs in less than 5% of cases. Treatment may be simple observation or may require removal of portions of the dead skin and fatty tissue. A gauze or vacuum dressing may be placed in the wound until it heals. Healing time will depend on the size of the area of skin necrosis.
- **Surgical site infection:** A surgical site infection is one that occurs in the skin or fatty tissue, in between the layers of the abdominal wall that are separated to repair the hernia, or inside the abdomen. This occurs in 5-20% of patients. Treatment may require antibiotics, opening of the incision, or placement of a needle or tube to drain the infection. If the incision is opened, a gauze or vacuum dressing may be placed in the wound until it heals. Healing time will depend on the size of the wound.
- **Mesh infection:** Infection may occur in the space where the mesh is located. This occurs in less than 5% of cases. Most often, this is treated exactly as other surgical site infection. However, if the infection does not go away, removal of the mesh may be needed. This is a rare.
- **Bowel injury:** Because we are working inside your abdomen, there is a risk of injury to your small or large intestine, which occurs in about 1% of cases. If this occurs and is seen at the time of surgery, it is repaired immediately. There is a small chance that a bowel injury could be missed, which may cause you to become seriously ill and likely require additional operation(s) to repair the bowel, prolonged hospital stay, or even result in death.

- Hernia recurrence: there is a 5-10% chance that your hernia will come back.

Any surgery has a risk of some complications, which may include:

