withdrawn from the study at any time if it is in the study Physician's judgment that withdrawal is in the participant's best interest, if the participant's medical condition changes or if the participant no longer follows the study instructions.

Informed Consent: The formal consent of a participant, using the GHS IRB approved informed consent form template, will be obtained by the study Physician before the participant undergoes any study procedures. The consent form will be signed and personally dated by the participant, a witness and the person who conducted the informed consent discussion. The original signed informed consent form will be retained in the participant's study records. A photocopy of the informed consent form will be scanned into the electronic system at the Vascular Health Alliance office. A photocopy of the signed informed consent form will be given to the participant for their records at the time of consent.

Safety and Reporting: Adverse Events, Serious Adverse Events and Unanticipated Adverse Device Effects will be reported to the GHS IRB according to OHRP policies 18.0 "Reporting of Unanticipated Problems Involving Risks to Subjects or Others and Adverse Events" and 40.0 Appendices "Reportable Event Reporting Requirements - Appendix A."

Protocol Deviations: Protocol Deviations will be reported to the GHS IRB according to OHRP policy 20.0 "Non-compliance with Regulations, IRB Policies, Procedures or Decisions."

Privacy and Confidentiality: All data for this study will be kept confidential.

Costs: This study is not expected to yield any additional costs to participants. Participants will not be compensated to participate in this study.

References:

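### A new adverse event must be reported by the patient to meet the protocol's definition, so new events first found by the surgeon, on examination, on imaging or in the laboratory fall outside it

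*Combined protocol and SAP*

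**What the plan says.** The Adverse Events paragraph, which follows the statistical analysis text, defines an adverse event as "any unfavorable or any unintended sign, symptom or disease that is reported by the patient to have occurred", and adds "or a worsening of a preexisting condition". On handling it says only "Adverse events will be recorded and detailed". It does not say who looks for events or by what means.

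Safety and Reporting then states: "Adverse Events, Serious Adverse Events and Unanticipated Adverse Device Effects will be reported to the GHS IRB according to OHRP policies 18.0", together with a second institutional policy. Serious adverse events and unanticipated adverse device effects are not defined in the document.

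Two other parts bear on the point. Data Collection lists registry (AHSQC) fields that include "technique for closure, use of component separation technique, and intraoperative complications", and adds "Hospital data will include LOS and any acute medical complications". The endpoint lists cover surgical site occurrences (SSO), surgical site infections (SSI), readmission and recurrence.

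**The concern.** For a new event, the wording makes the patient's report a condition of its being an adverse event. Several harms that the protocol itself lists under Potential Risks can come to light another way. Of bowel injury it says "If this occurs and is seen at the time of surgery, it is repaired immediately", and an anaesthetised patient reports nothing. A clot, an irregular heart rhythm or a pneumonia may first be found by a test or an examination.

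At stake is whether such events reach the adverse event record and, through it, the IRB. The trial compares a technique that the Background calls novel with an established one. A surgeon could enter a repaired bowel injury in the registry, follow the definition literally, and file no adverse event.

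**Working it through.** The protocol gives no adverse event count to reproduce. The check is a reading of the sections against each other, followed by the scale at the protocol's own rates.

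**1. Does the definition cover a clinician-found event?** It has two limbs.
- New sign, symptom or disease: qualified by patient report.
- Worsening of an existing condition: no reporter named, so a worsening that a clinician detects can qualify.

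A bowel injury made at surgery is new, so only the first limb is open to it, and that limb fails if the patient did not report it.

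**2. Does another section widen the definition?** Safety and Reporting names three classes of event and gives no definition of any. Potential Risks lists harms without calling them adverse events. Data Collection names complication fields without linking them to the adverse event record. Nothing widens it.

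**3. Where would each kind of event be recorded?**

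| Event first found by a clinician | Recorded as | Stated to be an adverse event? |
|---|---|---|
| Bowel injury seen at surgery | Registry: intraoperative complication | No |
| Clot or arrhythmia during the index stay | Registry: acute medical complication | No |
| Haematoma, seroma, wound infection | Endpoint (SSO or SSI) | No |
| Event leading to readmission; hernia recurrence | Endpoint | No |
| New non-wound event after discharge, no readmission | Not clearly anywhere; a procedure would appear in the cost data | No |

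**4. Scale.** Inputs: 100 patients (Participant Enrollment); bowel injury about 1% and thromboembolism about 2% (Potential Risks). Expected count = 100 × rate. Chance of at least one = 1 − (1 − rate)^100, with patients treated as independent.
- Bowel injury: 100 × 0.01 = 1 expected; 1 − 0.99^100 = 63%.
- Thromboembolism: 100 × 0.02 = 2 expected; 1 − 0.98^100 = 87%.

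These are totals for each harm, hence upper bounds. The protocol does not say what share would be found first by a clinician. That share could lie anywhere from none to all, so the expected number outside the definition is 0 to 1 for bowel injury and 0 to 2 for thromboembolism.

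**The case against.** The strongest reply is that little is lost. The registry holds intraoperative and in-hospital complications, the wound outcomes, readmission and recurrence are endpoints that do not depend on patient report, and visits run to 2 years. On this view the gap is a matter of labels. That largely stands, and it limits the point to classification and reporting plus the small remainder in the last row of the table. It does not answer the reporting gap, because no section says that a registry complication is an adverse event.

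A reader might infer four stronger things that the documents do not support.

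- *That only patient reports count.* The worsening limb names no reporter.
- *That 10 to 15 haematomas in 100 patients would be missed.* That is the protocol's total rate, and Composite Outcome names haematoma among the SSOs in the primary endpoint.
- *That the comparison between arms is biased.* No blinding is described, and Potential Limitations accepts that patients may hold views on robotic repair, so a count resting on patient report could be influenced. But no between-arm test of adverse events is planned, and the harms that are compared do not use this definition.
- *That IRB reporting must inherit the narrow wording.* The institutional policies may define events more broadly. They are not reproduced, so this cannot be settled either way. The Adverse Events paragraph does not defer to them, and within the document it is the only definition that staff have.

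**Conclusion.** The concern holds as a defect in the definition and in what it makes reportable. A new event that a clinician finds and the patient does not report fails the written definition, and the bowel injury described in Potential Risks is the plain example. The defect lies in a rule as stated, so it goes beyond missing detail.

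Its size is modest: about 1 bowel injury and at most about 2 thromboembolic events expected in 100 patients, plus an unquantified number of other non-wound events. This rests on the protocol's approximate rates, on full enrolment, and on a literal reading of the patient-report clause. The documents do not show that most of these events would go unrecorded. Sample size, endpoints and the primary analysis do not change.

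**What to change.** Make two changes of about one sentence each.

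1. In Adverse Events, keep both limbs and replace the patient-report condition with: reported by the patient or observed by the study team.
2. In Safety and Reporting, state that intraoperative and acute medical complications entered in the AHSQC count as adverse events for that section.

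No new procedures or visits are needed, but there would be more events to record. Observed seromas would qualify, at a stated rate of up to 50% of patients (up to 100 × 0.50 = 50), and so would haematomas at 10 to 15% (10 to 15 patients). Some of these would already be patient-reported, and one patient may have both, so the figures should not be added. Both can be taken from the endpoint records, since the secondary endpoint of all SSOs already requires them. Whether each would need its own report to the IRB depends on the institutional policies, which the sponsor should check when making the change.
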